Site Name: _____

Site Investigator: _____

Signed: _____ Date: _____

LIST OF ABBREVIATIONS

ALS	Amyotrophic Lateral Sclerosis
ALSAQ-40	Amyotrophic Lateral Sclerosis Assessment Questionnaire-40
C5	Complement component 5
CNS-BFS	Center for Neurologic Study Bulbar Function Scale
Covid-19	Coronavirus Disease 2019
FVC	Forced Vital Capacity
gMG	Generalized Myasthenia Gravis
IMNM	Immune-mediated Necrotizing Myopathy
IP	Investigational product
ITT	Intent-to-Treat
IV	Intravenous
OLE	Open Label Extension
PD	Pharmacodynamic
PK	Pharmacokinetic
RBC	Red blood cells
RSA	Regimen-Specific Appendix
SOC	Standard of care
SVC	Slow Vital Capacity
VC	Vital Capacity

REGIMEN-SPECIFIC APPENDIX SUMMARY

Regimen-Specific Appendix A

For 0.3mg/kg SC zilucoplan administered once daily and placebo

Allocation to Treatment Regimens

Participants must first be screened under the Master Protocol and before they are randomized to an RSA.

As soon as pre-defined criteria for futility for the RSA are met, or the target number of randomized participants has been reached, enrollment will stop in the RSA.

Number of Planned Participants and Treatment Groups

The number of planned participants for this regimen is approximately 160.

There are 2 treatment groups for this regimen, active and placebo. Participants will be randomized in a 3:1 ratio to active treatment or placebo (i.e., 120 active: 40 placebo).

Planned Number of Sites

Research participants will be enrolled from approximately 60 centers in the US.

Treatment Duration

The maximum duration of the placebo-controlled portion is 24 weeks.

Follow-up Duration

At the conclusion of the 24-week placebo-controlled period of the study, all participants will either schedule a 40-day follow up safety phone call and end their participation in the regimen or have the option to receive zilucoplan in the Open Label Extension phase of the study.

In the Open Label Extension, zilucoplan will be provided by Ra Pharmaceuticals, Inc. until zilucoplan is approved and available in the United States, or Ra Pharmaceuticals, Inc. terminates development of zilucoplan for ALS.

Total Planned Trial Duration

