- Efficacy Per-protocol (EPP) Set: The subset of participants in the FAS analysis set who initiated study treatment and who were not involved in protocol deviations that affected the scientific integrity of the trial as documented prior to data lock, classified according to the treatment they actually received. Inclusion or exclusion from the EPP analysis set of any participant for whom treatment assignment was unblinded prior to data lock will be governed by the prespecified criteria above. If a participant's data is truncated for inclusion in the EPP analysis set due to non-adherence to protocol-specified dosing, clinical events observed up to 40 days after the censoring event will be included in the EPP analysis set. For all other events leading to truncation of a participant's data, no events beyond that date will be included. Data from placebo participants shared from other regimens will not be truncated due to non-adherence to protocol-specified dosing.

Applicable analysis sets (FAS, EPP, and STF) will include shared placebo participants from regimens B, C, and D. Data from shared placebo participants will include visits and events that occurred on or before the date of the final placebo-controlled period follow-up of an RGA participant. As only concurrently enrolling regimens are contributing to efficacy analyses, the FAS and ECC analysis sets are synonymous and only the FAS analysis set will be referenced. As

RGA is the only regimen administering study drug by subcutaneous injection among those contributing to safety analyses, the ECM and ERO analysis sets and the STN and SRO analysis sets are synonymous and only the ERO and SRO analysis sets will be referenced.

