Treatment-dependent differences in the proportion of participants experiencing a given type of TEAE will not be tested. Treatment-dependent differences in TEAE incidence rates in units of number per 100 participant years will be estimated as differences rather than ratios and will include comparison-wise 95% confidence intervals with variance estimates obtained by the delta method.

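### Delta-method intervals for adverse-event rate differences treat a zero-event arm as having no uncertainty, so in the regimen-only safety set (120 v 40) they can lie wholly above zero up to about 15% of the time under no drug effect

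*SAP*

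**What the plan says.** SAP section 6.6.1 takes adverse-event summaries from the Master SAP, with revisions. One revision drops testing of proportions: "Treatment-dependent differences in the proportion of participants experiencing a given type of TEAE will not be tested". Another concerns incidence rates per 100 participant-years, whose between-arm differences "will be estimated as differences rather than ratios" and "will include comparison-wise 95% confidence intervals with variance estimates obtained by the delta method". The section gives no rule for zero or sparse counts, no minimum number of events and no alternative interval. It also does not say which safety set the rate differences use.

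Two safety sets are in play. Section 6.1 says "Applicable analysis sets (FAS, EPP, and STF) will include shared placebo participants from regimens B, C, and D", so STF is a pooled set; the number of shared placebo participants is not given. The same section explains that this is the only subcutaneous regimen among those contributing to safety analyses, so "only the ERO and SRO analysis sets will be referenced". SRO is the regimen-only safety set. Its planned size comes from the protocol summary: "The number of planned participants for this regimen is approximately 160", and "Participants will be randomized in a 3:1 ratio to active treatment or placebo (i.e., 120 active: 40 placebo". On follow-up, "The maximum duration of the placebo-controlled portion is 24 weeks".

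**The concern.** A delta-method variance for a rate is x/T², where x is the number of events and T the person-time. When x = 0 the variance is 0, so the interval treats the rate in that arm as known to be exactly zero. Working on the log scale and transforming back does not help: the rate squared times 1/x is again x/T², which tends to zero with x.

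With 3:1 allocation the empty arm will usually be the smaller placebo arm. The error therefore runs mostly one way, towards an apparent excess on zilucoplan. This matters because these intervals are the only between-arm inference on individual adverse events stated in this SAP, and an interval labelled 95% that excludes zero will be read as a safety signal. SRO is also where some comparisons have to be made. Injection site reactions are events of interest (SAP Appendix 1), and this regimen's own placebo group is the only contributing placebo group that received subcutaneous injections.

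**Working it through.** **Inputs from the documents.** 160 × 3/4 = 120 active and 160 × 1/4 = 40 placebo, which agrees with the protocol's stated arm sizes. The maximum placebo-controlled follow-up is 24 weeks (168 days). The interval is two-sided 95%, so 2.5% per tail.

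**Assumptions.** SRO is the set used; mean follow-up per participant is equal in the two arms; there is no dropout; counts are independent Poisson with equal true rates. Person-time is then 120 × 168/365.25 = 55.2 PY active and 40 × 168/365.25 = 18.4 PY placebo.

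**Interval.** x1/T1 − x0/T0 ± 1.96 × √(x1/T1² + x0/T0²). Multiplying through by T0 with T1/T0 = 3 gives (x1/3 − x0) ± 1.96 × √(x1/9 + x0). Whether zero is excluded therefore depends only on the two counts and the 3:1 person-time ratio. A longer window, such as the 40 days after last dose, or dropout similar in both arms, moves the event rate at which the peak occurs but not its height.

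**Zero placebo events.** The lower limit is above zero when x1/3 > 1.96 × √x1/3, that is, x1 > 1.96² = 3.84. So 4 v 0 is enough.
- 4 v 0: the planned interval is 0.1 to 14.3 per 100 PY. Under no effect all 4 events fall on active with probability 0.75^4 = 32%.
- 5 v 0: the planned interval is 1.1 to 17.0 per 100 PY, against −11.8 to 21.2 with Miettinen-Nurminen score limits. The corresponding probability is 0.75^5 = 24%.

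**Peak, by hand.** At 1.35 expected placebo events (4.05 expected active), P(x0 = 0) = e^(−1.35) = 0.259 and P(x1 ≥ 4) = 0.576. The product is 14.9%. Full enumeration over both counts gives 15.0%, so almost all of the error comes from samples with an empty placebo arm. The rate is 1.35/18.4 = 7.3 per 100 PY.

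**Enumeration across event rates, 120 v 40, equal true rates:**

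| True rate per 100 PY | Expected placebo events | Interval wholly above zero (nominal 2.5%) |
|---|---|---|
| 1 | 0.18 | 0.2% |
| 2 | 0.37 | 1.8% |
| 4 | 0.74 | 8.7% |
| 5 | 0.92 | 11.9% |
| 8 | 1.47 | 14.8% |
| 10 | 1.84 | 13.0% |
| 15 | 2.76 | 8.5% |
| 50 | 9.2 | 4.6% |

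The chance exceeds 10% between about 0.85 and 2.35 expected placebo events, or 4.6 to 12.8 per 100 PY. The opposite tail is 0.1% to 0.6% at 4 to 15 per 100 PY.

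**Robustness.** A binomial version with 120 v 40 peaks at 14.7%. Overdispersed counts (gamma frailty variance 1 and 3) peak at 15.2% and 15.8%.

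**Pooled set.** The shared placebo number is not given, so it is assumed. With 160 placebo participants the maximum chance of an interval wholly above zero is 2.2%; with 120 it is 2.7%. There is no excess of the kind seen in SRO.

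**Other limits at 120 v 40.** The maximum harm-side error is 1.9% for MOVER limits built from exact Poisson intervals, 2.2% for score limits and 2.6% for mid-P. With score limits and no placebo events, zero is excluded only when x1/3 > 3.84, which needs 12 v 0. Score limits also leave 3.1% to 3.9% on the false-protection side at 4 to 15 per 100 PY. The same enumeration puts the MOVER limits at 0.6% to 1.6% on that side.

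**The case against.** The strongest reply is that the set and the model are inferred. Section 6.6.1 does not name SRO; its use is suggested by section 6.1 and by other safety sections such as 6.6.6. The Master SAP, which is not available, could hold a sparse-count rule or fix the count model. This stands as a limit. However, the delta-method wording is in the regimen SAP, which section 1 makes authoritative over the Master SAP, and nothing in these documents supplies a zero-count rule.

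Second, 15% is a peak. For events rarer than about 2.2 per 100 PY the interval is below nominal on the harm side. A reader might infer that most preferred terms will have 0 to 2 placebo events and so fall in the bad range. The documents give no expected event frequencies, so that inference has no source.

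Third, nothing is decided by these intervals. They are comparison-wise, proportions are not tested, and the counts shown beside them let a reader see a 4 v 0. This also stands: here a signal means only that the interval excludes zero.

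Fourth, sensitivity to harm has value in a safety display for a drug with a recognised infection risk (protocol section 5.10.1), and better limits give some of it up. That is a real trade-off. But a 95% label on an interval that excludes zero at 4 v 0 misstates the uncertainty, and sensitivity obtained that way is not evidence.

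**Conclusion.** The point holds for the regimen-only comparison. At 120 v 40 the planned intervals can lie wholly above zero under no drug effect up to about 15% of the time against a nominal 2.5%. The excess persists at commoner rates (about 4.6% at 50 per 100 PY). This rests on SRO being the set used, equal mean follow-up in the two arms, and no sparse-count rule in the Master SAP.

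Two stronger readings are not supported. One is that adverse-event intervals across the whole safety analysis are distorted: the pooled set shows no such excess under 120 to 160 assumed placebo participants, and the rarest events are conservative even in SRO. The other is that the plan would declare false safety findings: it attaches no test, threshold or stopping rule to these intervals. The change is worth making because it is cheap and the error is one-sided; the efficacy conclusions are not affected.

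**What to change.** In SAP section 6.6.1, replace the delta-method clause with limits for a difference of Poisson rates that remain valid at zero counts, at least in SRO. Suitable choices are MOVER limits built from exact Poisson intervals, or exact or mid-P-based limits. Miettinen-Nurminen score limits are acceptable, with the false-protection error shown above. The same sentence should name the safety sets to which the rate differences apply.

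The cost is one SAP sentence and a macro change; the point estimates do not move. Intervals for sparse events become wider and asymmetric, and a handful of events against none will no longer exclude zero (score limits need 12 v 0). The sponsor should accept that loss knowingly and leave sparse findings to the listings and the clinical review of individual events.

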6.6.2 Safety Labs

Summaries and analyses of clinical safety labs are the same as specified in the M-SAP with the revision that lab results collected more than 40 days after last dose of study drug will not be tabulated, that abnormal levels will be classified to a toxicity grade based on quantitative grading using National Cancer Institute (NCI) Common Terminology Criteria for Adverse Events (CTCAE) version 5.0 and with the addition that maximum toxicity over all post-baseline assessments that occur within 40 days or fewer after last dose of study drug will be included in shift tables along with visit-specific shifts.

6.6.3 ECG Results

Summaries of ECG parameters and findings are the same as specified in the M-SAP with the revision that ECG parameters and findings collected more than 40 days after last dose of study drug will not be tabulated.

6.6.4 Vital Signs and Weight

Summaries and analyses of vital signs and weight are the same as specified in the M-SAP with the revision that vital signs and weight collected more than 40 days after last dose of study drug will not be tabulated.

6.6.5 Suicidality

Summaries of suicidality are the same as specified in the M-SAP with the revision that suicidality noted more than 40 days after last dose of study drug will not be tabulated.

6.6.6 Immunogenicity

The proportion of participants positive, negative, and missing for ADA and anti-PEG-ADA immunogenicity endpoints will be summarized by treatment group and visit and at any post-baseline visit that occurs within 40 days or fewer after last dose of study drug in the SRO analysis set.

Additional immunogenicity analyses are described in Appendix 2 of this R-SAP. These additional analyses will be performed by UCB Ra Pharma and reported in a separate immunogenicity report.

6.7 Other Analyses

6.7.1 Participant Disposition

All participants consented to the Master Protocol between the time of the first and last consent of a participant assigned to a regimen included in the FAS analysis set will be summarized as a single set for the following events: consented to the Master Protocol, failed screening for the Master Protocol, other reasons not assigned to a regimen (including timing out of the screening window, death, withdrawal of consent, early termination, and administrative termination), and assigned to a regimen. Reasons for Master Protocol screen failure will be summarized.

All participants in the above sample assigned to a regimen will be summarized as two sets (final screening for RGA vs. final screening for a non-RGA regimen) for the following events: consented to a regimen, failed screening for a regimen, other reasons not randomized within a regimen (including timing out of the screening window, death, withdrawal of consent, early termination, and administrative termination), and randomized within a regimen. If a given individual is screened multiple times prior to randomization within a regimen, then the final screening experience of that individual will be summarized. Reasons for RGA screen failure will be summarized separately for all participants screened for RGA whether that was their final screening experience or not.

All participants in the FAS analysis set will be summarized as two sets (randomization to active study drug vs. randomization to placebo) for the following events: initiated regimen-specific study drug, prematurely terminated study participation due to death, withdrawal of consent, early termination, loss to follow-up, or administrative termination, completed 24-week follow up, and

completed a safety follow-up visit vs. continued into the OLE. Reasons for withdrawal of consent or early termination after randomization will be summarized.

Any randomized participants excluded from the FAS and EPP analysis sets or included in the FAS analysis set but not contributing to the primary analysis will be identified in a listing together with the reason for their exclusion.

6.7.2 Study Drug Compliance and Tolerance

Summaries of study drug compliance and tolerance are the same as specified in the M-SAP with the clarification that summaries will be reported for the ERO and SRO analysis sets and that date of permanent discontinuation of study drug is the date of last use of double-blind study drug among all participants in a given analysis set.

The number of days of exposure to study drug will be calculated in three ways:

- as the number of days from dose initiation to the final safety assessment during the placebo-controlled period, inclusive,
- as the number of days from dose initiation to drug withdrawal, inclusive, less any interval during which use of study drug was interrupted (individual missed doses will not be subtracted unless noted in the dosage management log), and
- as the number of days from dose initiation to the earlier of final contact during the placebo-controlled period or 40 days after last dose of study drug, inclusive.

6.7.3 Concomitant Medication Use

Summaries of concomitant medication use are the same as specified in the M-SAP.

6.7.4 Medical History

Medical histories will be summarized by MedDRA system organ class, high level term, and preferred term in the STF and SRO analysis sets.

6.7.5 Blindedness

The proportions of participants and site investigators who report on the Exit Questionnaire a guess of active vs. placebo treatment assignment, each level of surety of that guess, and each of five pre-specified reasons for making a treatment assignment will be summarized by treatment group in the FAS, ERO, and EPP analysis sets. Treatment-dependent differences in the proportion guessing active treatment assignment will be tested among all respondents and among those stating they are at least somewhat sure of their guess by Fisher's exact test and the difference in proportion guessing active treatment assignment will be estimated with confidence bounds.

6.7.6 Protocol Deviations

The number of major and minor protocol deviations will be summarized by type of deviation and treatment group in all analysis sets. Listings of all protocol deviations will be produced.

6.7.7 Impact of COVID-19 Pandemic

The proportions of planned assessments missed due to COVID-19 restrictions or disruptions will be summarized by treatment group, visit, and type of assessment in the FAS and ERO analysis sets. Protocol deviations that resulted from COVID-19 restrictions or disruptions will be

summarized by treatment group and type of deviation in the FAS and ERO analysis sets and listed.

7. Validation

7.1 Primary Efficacy Analysis

Validation of the primary efficacy analysis is the same as specified in the M-SAP.

Appendix 1. Treatment-emergent Adverse Events of Interest

Events	MedDRA Search Strategy
Infections	SOC “Infections and infestations”
Neisseria infections	HLT “ Neisseria infections”
Potential anaphylactic reactions	Potential anaphylactic reactions are defined via a MedDRA algorithmic approach, which combines a number of different TEAEs/ anaphylactic reaction symptoms that are reported on the same day or on 2 consecutive days, under the condition that use of study drug was still ongoing at the first of these 2 days. Some cases are dependent on the presence of multiple symptoms/ TEAEs and these multiple TEAEs must be on the same onset day or on 2 consecutive days, in order to be classified as an anaphylactic reaction; at least one of the symptoms/TEAEs needs to be serious for the reaction to be classified as a serious anaphylactic reaction. For cases dependent on multiple symptoms the onset date of the reaction will be the onset date of the first preferred term/ symptom experienced, whilst the onset date of serious reactions will be set to the date of the first serious preferred term/symptom. When the reaction consists of multiple TEAEs of different severities, the severity of the reaction is the maximum (i.e., most severe) severity. Similarly, a reaction is classified as related by the investigator if at least one TEAE is related.
Hypersensitivity reactions	SMQ “Hypersensitivity (narrow scope)”
Injection site reactions	TEAEs in MedDRA HLT “Injection site reactions” or HLT “Administration site reactions NEC”.
Drug related hepatic disorders	Narrow SMQ of “Drug related hepatic disorders - comprehensive search (SMQ)” excluding the 2 sub-SMQs of “Liver neoplasms, benign (incl. cysts and polyps) (SMQ)” and “Liver neoplasms, malignant and unspecified (SMQ)”
Malignant or unspecified tumours	SMQ “Malignant or unspecified tumours (SMQ)”
Malignant tumours	SMQ “Malignant tumours (SMQ)”

MedDRA Algorithmic Approach to Anaphylaxis

The standardized MedDRA query (SMQ) “Anaphylactic reaction” consists of three parts:

A narrow search containing PTs that represent core anaphylactic reaction terms:

- **SMQ** Anaphylactic reaction (SMQ)
 - ⊕ **PT** Anaphylactic reaction
 - ⊕ **PT** Anaphylactic shock
 - ⊕ **PT** Anaphylactic transfusion reaction
 - ⊕ **PT** Anaphylactoid reaction
 - ⊕ **PT** Anaphylactoid shock
 - ⊕ **PT** Circulatory collapse
 - ⊕ **PT** Dialysis membrane reaction
 - ⊕ **PT** Kounis syndrome
 - ⊕ **PT** Shock
 - ⊕ **PT** Shock symptom
 - ⊕ **PT** Type I hypersensitivity

A broad search that contains additional terms that are added to those included in the narrow search.

These additional terms are signs and symptoms possibly indicative of anaphylactic reaction and categorized in B, C or D:

Category B: Upper Airway/Respiratory

⊕ PT Acute respiratory failure⊕ PT Asthma⊕ PT Bronchial oedema⊕ PT Bronchospasm⊕ PT Cardio-respiratory distress⊕ PT Chest discomfort⊕ PT Choking⊕ PT Choking sensation⊕ PT Circumoral oedema⊕ PT Cough⊕ PT Cyanosis⊕ PT Dyspnoea⊕ PT Hyperventilation⊕ PT Irregular breathing⊕ PT Laryngeal dyspnoea⊕ PT Laryngeal oedema⊕ PT Laryngospasm⊕ PT Laryngotracheal oedema	
⊕ PT Mouth swelling⊕ PT Nasal obstruction⊕ PT Oedema mouth⊕ PT Oropharyngeal spasm⊕ PT Oropharyngeal swelling⊕ PT Respiratory arrest⊕ PT Respiratory distress⊕ PT Respiratory dyskinesia⊕ PT Respiratory failure⊕ PT Reversible airways obstruction⊕ PT Sensation of foreign body⊕ PT Sneezing⊕ PT Stridor⊕ PT Swollen tongue⊕ PT Tachypnoea⊕ PT Throat tightness⊕ PT Tongue oedema⊕ PT Tracheal obstruction⊕ PT Tracheal oedema⊕ PT Upper airway obstruction⊕ PT Wheezing
--	---

Category C: Angioedema/Urticaria/Pruritus/Flush

   Allergic oedema	   Pruritus
   Angioedema	   Pruritus allergic
   Erythema	   Pruritus generalised
   Eye oedema	   Rash
   Eye pruritus	   Rash erythematous
   Eye swelling	   Rash generalised
   Eyelid oedema	   Rash pruritic
   Face oedema	   Skin swelling
   Flushing	   Swelling
   Generalised erythema	   Swelling face
   Injection site urticaria	   Urticaria
   Lip oedema	   Urticaria papular
   Lip swelling	
   Nodular rash	
   Ocular hyperaemia	
   Oedema	
   Periorbital oedema	

Category D: Cardiovascular/Hypotension

   Blood pressure decreased
   Blood pressure diastolic decreased
   Blood pressure systolic decreased
   Cardiac arrest
   Cardio-respiratory arrest
   Cardiovascular insufficiency
   Diastolic hypotension
   Hypotension

An algorithmic approach which combines a number of anaphylactic reaction symptoms in order to increase specificity. A potential anaphylactic reaction is defined as meeting at least one of the following criteria where the different terms occur on either the same day as when an injection was administered or one day after:

A narrow term or a term from Category A;

A term from Category B - (Upper Airway/Respiratory) AND a term from Category C - (Angioedema/Urticaria/Pruritus/Flush);

A term from Category D - (Cardiovascular/Hypotension) AND [a term from Category B - (Upper Airway/Respiratory) OR a term from Category C - (Angioedema/Urticaria/Pruritus/Flush)]

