2.7 Treatment Administration

Zilucoplan and placebo are supplied as a sterile, preservative-free, aqueous solution prefilled into 1 mL glass syringes with 29-gauge, ½-inch, staked needles as a self-administration device. One

of three dosage strengths of zilucoplan will be supplied based on the weight of each participant at screening to achieve a dosage of approximately 0.3 mg/kg as specified in the table below.

Nominal Target Dose (mg/kg)	Actual Dose (mg)	Injection Volume (mL)	Weight Range (kg)	Dose Range (mg/kg)
0.3	16.6	0.416	≥43 to <56	0.30 to 0.39
0.3	23.0	0.574	≥56 to <77	0.30 to 0.41
0.3	32.4	0.810	≥77 to 150	0.22 to 0.42
Placebo	0.0	0.574	All weights	0.00 to 0.00

Participants with a screening weight less than 43 kg or equal to or greater than 150 kg will be accommodated on a case-by-case basis, in consultation with the Medical Monitor.

Study drug is administered subcutaneously into the abdomen once daily at approximately the same time each day by self-administration or with the assistance of a caregiver.

Additional details of treatment administration are described in the RGA RSA.

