6.1 Analysis Sets

The ITT analysis set is henceforth referred to as the Full Analysis Set (FAS) and defined as follows:

- Full Analysis Set (FAS): Participants who were randomized within RGA plus placebo participants from specified regimens, classified according to their randomized treatment assignment. Observations made after premature permanent discontinuation of study drug are included in this sample, should such participants remain on study. Observations completed after regimen data lock are excluded. Participants determined to not meet ALS diagnostic criteria are excluded.

The definition of the STF analysis set is revised as follows:

- Safety Full (STF) Set: Participants who initiated treatment within RGA plus placebo participants from specified regimens who are not known to be ineligible for RGA and who initiated treatment in their respective regimen, classified according to the treatment they actually received. Observations made after premature permanent discontinuation of study drug are included in this sample, should such participants remain on study. Observations completed after regimen data lock are excluded.

An analysis set restricting shared placebo participants to those regimens in which study drug is administered by the same route as RGA is defined as follows:

- Efficacy Common Mode of Administration (ECM) Set: The subset of participants in the FAS analysis set who are in regimens in which study drug is administered by the same route as RGA.

The definitions of the ECC, ERO, STN, and SRO analysis sets are the same as described in the M-SAP with reference to the ITT analysis set now referencing the FAS analysis set. The following analysis set is specific to RGA:

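### Appendix 1 ties potential anaphylactic reactions to an injection in one place and to ongoing study drug in another; read literally, the injection condition leaves out shared placebo participants who are not injected

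*SAP*

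**What the plan says.** **Who is pooled.** SAP section 6.1 builds the STF set from participants who started treatment in RGA, "plus placebo participants from specified regimens who are not known to be ineligible for RGA and who initiated treatment in their respective regimen". It adds: "Applicable analysis sets (FAS, EPP, and STF) will include shared placebo participants from regimens B, C, and D". The same section says that "RGA is the only regimen administering study drug by subcutaneous injection among those contributing to safety analyses", and concludes from this that "the STN and SRO analysis sets are synonymous and only the ERO and SRO analysis sets will be referenced".

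**How the event is defined.** SAP Appendix 1 states the timing twice.

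- The table row for potential anaphylactic reactions looks for symptoms on one day or two consecutive days, "under the condition that use of study drug was still ongoing at the first of these 2 days".
- The algorithm text that closes the anaphylaxis part of the appendix asks for terms "on either the same day as when an injection was administered or one day after". A narrow (core anaphylaxis) term qualifies alone. A respiratory term (Category B) needs a skin or oedema term (Category C) with it. A cardiovascular term (Category D) needs a B or a C term.

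**How RGA is dosed.** SAP section 2.7: "Study drug is administered subcutaneously into the abdomen once daily".

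**What is reported.** SAP section 6.6.1 summarises the TEAEs of interest, also by severity and for serious events. It rules out tests on TEAE proportions but plans differences in TEAE rates per 100 participant-years with 95% confidence intervals. It names no analysis set for these outputs; apart from listed revisions it relies on the Master SAP, which is not among the documents.

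**The concern.** A safety definition should find the event equally well in both groups being compared. The closing text depends on an injection, which is a feature of RGA's route and not of active treatment. In RGA, active and placebo participants both inject daily, so the condition hardly excludes anyone. In the STF set most of the placebo group may come from regimens where that condition cannot be met.

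Those participants would stay in the placebo denominator and add nothing to the numerator. An STF table could then show more potential anaphylactic reactions on zilucoplan than on placebo with no true difference. For a daily injected peptide, such an excess would draw attention.

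**Working it through.** **1. The two conditions side by side**

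| | Table row | Closing algorithm text |
|---|---|---|
| Gap between symptoms | One day or two consecutive days | None stated |
| Exposure condition | Study drug ongoing on the first day | Injection that day or the day before |
| RGA participant, injected daily | Can be met | Exposure met on nearly every on-drug day |
| B–D placebo participant, not injected | Can be met | Cannot be met |

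The exposure conditions nearly agree within RGA and separate for shared placebo. The symptom windows do not agree even within RGA. Under daily dosing, the closing text taken alone would let a cough in week 2 and a rash in week 20 qualify together; the table row would not.

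**2. Inputs**

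- RGA allocation (Protocol, Regimen-Specific Appendix Summary): about 160 at 3:1. 160 × 3/4 = 120 active and 160 × 1/4 = 40 placebo, which reproduces the stated split. All are assumed to start treatment.
- S, shared placebo participants not given injections: not stated. Assumed 40 to 160.
- p, the probability of the symptom pattern while on study drug: not stated. Assumed 1% to 5% and equal in every participant, so there is no true treatment effect.

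**3. Formula**

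- Table-row rule: STF placebo proportion = p.
- Literal injection rule: STF placebo proportion = p × 40/(40+S).
- Spurious excess on active = p × [1 − 40/(40+S)].

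If a further I shared placebo participants were injected by another route, the factor would be (40+I)/(40+I+S), which is closer to 1.

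**4. Results under the literal injection rule**

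| Assumed S | Factor | Excess, p = 1% | Excess, p = 2% | Excess, p = 5% |
|---|---|---|---|---|
| 40 | 0.50 | 0.50 points | 1.00 | 2.50 |
| 80 | 0.33 | 0.67 | 1.33 | 3.33 |
| 120 | 0.25 | 0.75 | 1.50 | 3.75 |
| 160 | 0.20 | 0.80 | 1.60 | 4.00 |

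**5. One case in full (p = 2%, S = 120)**

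- Active: 0.02 × 120 = 2.4 expected events, 2.0%.
- STF placebo, table-row rule: 0.02 × 160 = 3.2 events, 2.0%.
- STF placebo, literal injection rule: 0.02 × 40 = 0.8 events in 160, 0.5%.
- Spurious excess 1.5 points; ratio 2.0/0.5 = 4.
- As rates, with full 24-week follow-up and one event per affected participant: 24 × 7/365.25 = 0.460 years, so 2.0/0.460 = 4.35 against 0.5/0.460 = 1.09 per 100 participant-years.

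**6. SRO set.** With no shared placebo, S = 0 and the factor is 40/40 = 1.

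**The case against.** The best defence is that the table row is the definition and the closing text only describes the algorithm. A programmer who follows the row counts shared placebo participants like anyone else, and nothing is lost. The two statements can also be read as complementary. This stands to the extent that a reader might infer that the plan forces shared placebo participants to be non-events; the documents do not support that, because it follows from only one of two conditions. It does not remove the problem. The row refers to an algorithm, the closing text is that algorithm, and programming it as written, alone or together with the row, requires an injection.

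Other limits also stand:

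- A reader might infer that B–D participants never receive an injection. Section 6.1 excludes only subcutaneous study drug, and the closing text does not say whose injection is meant.
- A reader might infer that matches in placebo are to be expected because cough, dyspnoea and respiratory failure are on the Category B list. Those terms qualify only with a C or D term, and no event rate is given. Matches are possible; their number is unknown and could be zero.
- A reader might extend the point to injection site reactions. Their search has no injection-timing condition and also takes in a general administration-site term, so the argument does not carry over.
- The affected STF table is not shown to exist, since the analysis set comes from the Master SAP. SRO remains a referenced set.
- Proportions are not tested, and no efficacy conclusion depends on this output.

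**Conclusion.** The point holds as an unreconciled definition that can bias one descriptive safety comparison. If the closing text is programmed literally and an STF summary is produced, the placebo proportion is understated by a factor of 40/(40+S): 0.50 to 0.20 for assumed S of 40 to 160. For assumed p of 1% to 5%, the spurious excess on active is 0.5 to 4.0 percentage points. The direction is against the drug.

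The size rests on the assumed S, on equal background rates in injected and non-injected participants, and on none of the shared placebo participants being injected by another route. The SRO comparison is unaffected. This is a minor point, worth settling because the correction is small and affects how a safety signal would be read.

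**What to change.** Merge the two statements in Appendix 1 into one definition that:

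- keeps the table row's window between symptoms (one day or two consecutive days);
- replaces the injection condition with a route-neutral one, either a dose of study drug in the participant's own regimen or study drug ongoing;
- applies identically to every regimen in the set.

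Replacing both statements with a dose-timed condition alone would not do, because it drops the limit on the gap between symptoms.

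Alternatively, state in section 6.6.1 that potential anaphylactic reactions are compared between groups only in the SRO set.

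The first option costs a phrase in Appendix 1 and the matching program change, and would change what an STF table reports. The second costs one sentence and possibly one fewer STF table. Neither needs new data.
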